An Epic Dashboard will be used to screen eligibly patients using the following criteria:

- Admitted to the following units: 4 North, 4 South, 4 East, 4 Med Center East
- Age ≥ 18 years
- Problem list containing the following ICD10 codes: O10, O11, O12, O13, O14, O15, O16
- Preferred language is English

ENROLLMENT

Patients will be approached for enrollment in the study in their private hospital rooms. Research personnel will discuss potentially eligible patients with either the bedside nurse or charge nurse prior to approaching patients to determine any concerns about enrollment.

Recruiting Script: "Hello Ms. [Patient Last Name]. I am [Research Assistant Name] and I am a research assistant at Vanderbilt. I was hoping to talk to you about a study we are doing among patients who have had high blood pressure issues during pregnancy or postpartum."

Patients Who Express Interest: "We want to learn how to better help patients who have high blood pressure in pregnancy. All women who have high blood pressure in pregnancy should see their obstetric provider within one week of leaving the hospital to watch blood pressure closely. We want to learn the best way to provide blood pressure care. If you join the study, you would be placed randomly into a group. You would either see your OB as usual for blood pressure help or manage your blood pressure electronically with help from a special team. You would still see your OB for regular postpartum follow up and questions. You would also be grouped by different blood pressure goals. As part of the study, we will look at your health record to learn about your delivery and any health issues. We only share this information with the research team and not your OB. You will get \$50 if you finish all 3 months of the study. Risks of the study are small but could include over-treatment, meaning that medication to control blood pressure may be given without added benefit to you, and sharing of health information by accident."

Once a patient expresses interest in participating, they will be given the informed consent document electronically delivered (via text web-link or email link to RedCap) and their e-signature will be obtained if they consent to participation.

STUDY PROCEDURES

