- ▶ **Survey 3**: (12-weeks after delivery): Participants will be contacted via SMS text or email to ask about follow up with a primary care physician and chronic hypertension. Participants will receive a \$20 gift card for completion of this survey.

OUTCOMES

Primary Outcomes: The outcome for the R21 and listed on ClinicalTrials.gov is the proportion of patients with a blood pressure recorded in the office at 7-10 days postpartum (**BPinperson**). It is not hypothesized that the primary outcome varies by the blood pressure control intervention but will vary by the blood pressure management intervention.

Secondary Outcomes: We will examine three categories of secondary outcomes (**Table 3**). *Hypertension control and adverse events* includes measures of blood pressure control and events potentially associated with poor blood pressure control such as severe maternal morbidity (SMM) and hospital readmission. Given that our intervention tests different models of care, we will assess *health care utilization* associated with these models including adherence to in-person and remote blood pressure monitoring, medication use, attendance at scheduled visits, and unscheduled visits to an urgent care or emergency room.

We will also examine a variety of *patient-reported outcome measures* especially satisfaction with care. HDP carries not only a risk of long-term health sequelae, but also post-traumatic stress disorder, depression, and anxiety.^{92,93} In a review of patients' experiences with HDP, the potential for worsening or chronic hypertension was associated increased feelings of anxiety and loss of agency.⁹⁴ We hypothesize that augmented remote monitoring and tighter blood pressure control, both individually and in combination, will improve postpartum blood pressure control within the first six weeks postpartum. We also hypothesize that participants, especially Black participants, will find the results of these interventions satisfying and acceptable as they provide a nexus of agency during otherwise stressful life events. Observed reductions in blood pressure provide more frequent and immediate feedback to participants relative to other meaningful outcomes such as SMM or hospital readmission. We also acknowledge the possibility that patients also could find frequent observation of blood pressures and tighter parameters to be burdensome or increase anxiety about health status.

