Primary care visit attendance (%)	10%	43%
Diastolic dysfunction: Mean early diastolic filling or e' (SD)	11.7 (3.1)	1.24

DATA AND SAFETY MONITORING

Data will be entered directly into the Research Electronic Data Capture (REDCap) site, a secure web platform for building and managing online databases and surveys with flexible design of electronic CRFs. REDCap is compliant with the Health Insurance Portability and Accountability Act and includes password protection. REDCap maintains records of all changes made to databases so that investigators can identify deleted data and changes made. Each person accessing REDCap has an individual ID for security tracking and to prevent unauthorized access to data. Data can be exported to common statistical analysis packages (e.g., SAS, R, and Stata) and protected health information removed. Several internal quality checks are available in REDCap including: automatic range checks for numeric variables and creation of automatic data reports that help identify data that appears inconsistent, incomplete, or inaccurate. Every two weeks, a separate clinical trials associate assigned to support the study will audit 3 randomly selected charts to ensure that data have been entered correctly and for continuous process improvement. After obtaining informed consent, a copy of the consent form will be sent to participants via email or text and all information retained in the REDCap database. The REDCap database is encrypted and can only be accessed by research personnel with appropriate clearance.

For this study, an adverse event (AE) is defined as any untoward medical occurrence associated with the study, whether or not considered intervention- or procedure-related. An AE can therefore be any undesirable or unintended sign, symptom, laboratory testing or diagnostic imaging finding, or disease temporally associated with participation in the study, without any judgement about causality. The determination of the relationship between the AE and the study procedures must be made by the PI or their designee. This definition will also include changes in the participant medical status that may be related to the study procedures. Maternal medical conditions that are present prior to consent can be considered as baseline and not reported as AEs. However, if the participant's condition deteriorates at any time during the study, it will be recorded as an AE.

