The PI will monitor protocol adherence and the progress of the trial on an ongoing basis by reviewing all data collected and monitoring enrollment and follow up. For participants who indicate a high degree of dissatisfaction with the study, the PI will contact the participant to assess the source of the dissatisfaction and whether any postpartum complications have arisen. If complications are uncovered and the participant requires medical care, we will facilitate obtaining care with our providers at Vanderbilt. The PI will notify the Vanderbilt University's Institutional Review Board (IRB) of any AEs promptly and at most within 7 days of the event. If the adverse event is thought to be due to the study, the PI will draft a safety report and send a copy to the IRB who serves as an objective review mechanism. This policy/procedure means that any potential conflict of interest inherent in the PI being the sole reviewer of serious adverse events is avoided. In addition, all research personnel will be asked to contact the PI within 24 hours to report serious adverse events. All SAEs occur during the study defined by the given protocol, regardless of the relation to the research, will be reported to the IRB by telephone, e-mail or fax within 24 hours of the investigator's awareness of the occurrence of the event. All expected non-serious adverse events (i.e. patient dissatisfaction) that occur at a greater frequency or severity than anticipated and all unexpected non-serious adverse events will be reported to the IRB within 15 working days of the investigator becoming aware of the event. Adverse events will be summarized annually in the IRB application for continuation or termination of the research.

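### The only frequency-based safety rule names patient dissatisfaction as the sole expected adverse event, and no comparison of harm by arm or review threshold is prespecified

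*Combined protocol and SAP*

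**What the plan says.** All of the safety rules stand in Data and Safety Monitoring.

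- **Definition.** An adverse event is "any untoward medical occurrence associated with the study, whether or not considered intervention- or procedure-related".
- **Frequency rule.** The IRB is told of "All expected non-serious adverse events (i.e. patient dissatisfaction) that occur at a greater frequency or severity than anticipated". No anticipated frequency or severity appears anywhere in the document.
- **Contact rule.** "For participants who indicate a high degree of dissatisfaction with the study, the PI will contact the participant", to find the source of the dissatisfaction and "whether any postpartum complications have arisen".
- **Individual reporting.** "The PI will notify the Vanderbilt University's Institutional Review Board (IRB) of any AEs promptly and at most within 7 days of the event". Serious events go to the IRB within 24 hours of awareness, whatever their cause. Unexpected non-serious events go within 15 working days of awareness. An event thought due to the study also gets a safety report.
- **Aggregate review.** The PI reviews all collected data on an ongoing basis. In addition, "Adverse events will be summarized annually in the IRB application for continuation or termination of the research".

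Elsewhere, the recruiting script under Enrollment tells patients: "Risks of the study are small but could include over-treatment, meaning that medication to control blood pressure may be given without added benefit to you". Under Secondary Outcomes the hypothesis is that participants, Black participants especially, "will find the results of these interventions satisfying and acceptable".

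**The concern.** The trial starts or titrates antihypertensives to a lower target in half of its participants and, in the remote arms, moves that decision to a navigator. The safety question that this raises is comparative: does either factor produce more medical harm than its control? The one rule that looks at how often something happens is tied to an event that is not a medical harm, and it has no reference rate, so it cannot be applied even to that event. Over-treatment, the treatment risk disclosed to patients, is not mentioned in the safety section.

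The contact rule has a second weakness. Satisfaction is expected to respond to the interventions, and the protocol also allows that tighter parameters and frequent readings may be burdensome. The share of women asked about complications by this route can therefore differ by arm for reasons unrelated to safety, in a direction that cannot be known beforehand.

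**Working it through.** **1. Which routes depend on dissatisfaction, and which compare arms?**

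| Route in Data and Safety Monitoring | Depends on dissatisfaction? | By-arm comparison or threshold stated? |
|---|---|---|
| Any AE to IRB, 7 days from event | No | No |
| SAE to IRB, 24 hours from awareness | No | No |
| Safety report if thought due to the study | No | No |
| Unexpected non-serious AE, 15 working days from awareness | No | No |
| Expected non-serious AE, more frequent or severe than anticipated | Yes, the only event named | No anticipated rate given |
| PI contact asking about complications | Yes | No |
| Ongoing PI review of all data | No | No |
| Annual AE summary to IRB | No | No |

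Most routes work without dissatisfaction. None is stated to compare arms.

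**2. Clocks.** An unexpected non-serious event is also one of "any AEs" in the ordinary sense of the 7-day rule, so it carries two deadlines: 7 days from the event, and 15 working days (15/5 = 3 weeks, about 21 calendar days) from awareness. Both the length and the starting point differ.

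**3. What a by-arm count could add.** The documents give no event rate, so there is no stated figure to reproduce and every rate below is an assumption.

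Inputs: 1,404 enrolled over 4 years (Table 5), so 1404/4 = 351 a year and 351/2 = about 175 per BP goal a year. Cumulative numbers per goal at years 1 to 4 are 175, 351, 527 and 702.

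Expected cumulative events = n × rate. At 3% v 6%:
- year 1: 175 × 0.03 = 5 v 175 × 0.06 = 10
- year 2: 351 × 0.03 = 11 v 351 × 0.06 = 21
- year 4: 702 × 0.03 = 21 v 702 × 0.06 = 42

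Rule tested: one-sided Fisher exact p<0.05 for an excess under tight control, on the cumulative count at each annual look, with 20,000 simulated trials.

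| Assumed rate, standard v tight | Prompt by year 1 | Year 2 | Year 3 | Year 4 |
|---|---|---|---|---|
| 2% v 4% | 18% | 41% | 59% | 72% |
| 3% v 6% | 29% | 57% | 76% | 87% |
| 5% v 10% | 48% | 80% | 93% | 98% |

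If the annual summary were pooled, an assumed 2% v 6% would appear only as (2 + 6)/2 = 4%.

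**4. False alarms over four looks, equal rates of 2-5% in both groups.**
- BP goal only, one composite: about 7-8%.
- Both factors, one composite: about 13-16%.
- Four event classes tested separately on both factors, assumed independent: above 40%. For example, 1 − (1 − 0.13)^4 = 43%.

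**5. A count to avoid.** Adverse events recorded while on antihypertensives will be more numerous where more women are treated. If 40% v 60% are treated (assumed) and the event rate among treated women is the same 5-10%, the same rule fires in about 35-56% of trials with no higher risk per treated woman.

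**The case against.** A reader might infer that an excess of harm in one arm would trigger no review over the 4 years. The text does not support that. Every adverse event is reportable, serious events go to the IRB within a day regardless of cause, the PI reviews data throughout, and the IRB receives an annual summary for its decision on continuing.

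A reader might also infer that the annual summary cannot show a difference between arms. The protocol does not say that the summary is pooled. It only fails to require a split.

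Nor can one say that a satisfied woman with a complication goes unnoticed. An in-person blood pressure check is requested for everyone, and readmission, severe maternal morbidity and urgent visits are Table 3 outcomes for all. Remote-arm women hear from the navigator each weekday in weeks 1-2 and at least weekly in weeks 3-6. What is absent is one complications question put uniformly to all arms.

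Finally, dissatisfaction with the study is close to, but not the same as, the Table 3 items, which ask about postpartum care and remote monitoring. Several medical events that could be tabulated are also Table 3 outcomes, so overlap with an outcome is not in itself the fault. The fault is that the named event is not a medical one.

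These points limit the consequence. They leave the missing comparison, the unusable frequency rule, the selective question and the conflicting clocks in place.

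**Conclusion.** The point stands in a limited form. Harm reaches the IRB event by event and in an annual summary, but the plan prespecifies no comparison by randomised arm and no threshold for review. Its one frequency rule rests on a non-medical event without a reference rate. Its one rule for the PI to ask about complications selects women on a response that the interventions are expected to change. The two clocks for unexpected non-serious events cannot both be the operative rule.

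The size depends on event rates that the documents do not give. For a doubling from an assumed 2-5%, a simple annual by-arm count would prompt review by year 4 in 72-98% of trials. At the low end it is a modest tool: 41% by year 2 for 2% v 4%. This should be corrected, but it does not threaten the primary analysis.

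**What to change.** In Data and Safety Monitoring:

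1. Remove dissatisfaction as the definition of expected adverse events and treat it as a patient-reported outcome.
2. In the existing annual IRB summary, tabulate one prespecified composite of medical events (for example SAEs including severe maternal morbidity). Show it cumulatively by BP goal and by monitoring arm, with all randomised women as the denominator. State a threshold, such as a one-sided exact p<0.05 excess, that prompts IRB review and nothing more. Do not count events only while on treatment. Read the monitoring comparison knowing that closer contact in the remote arms may raise detection.
3. Put the complications question to every participant in Survey 2. Table 5 expects 1,053 of 1,404 to be retained at 6 weeks, so about 351 may not answer, and the composite should not depend on the survey.
4. Reconcile the 7-day and 15-working-day rules, including whether the clock starts at the event or at awareness.

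The cost is protocol wording, one table a year, one survey item, and the chance of an unnecessary IRB review over four looks: about 7-8% if only the BP goal is tested, 13-16% if both factors are, at assumed event rates of 2-5%. No new committee or visit is needed.

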APPENDIX A

Blood pressure cuff fitting

Arm circumference to be measured and recorded in REDCap along with size of cuff provided

1. AC 17-22cm: small size cuff
2. AC 23-42cm: wide range size cuff
3. AC 43-50cm: extra large adult size cuff

APPENDIX B: Epic MyHealth Message for Intervention #1 (Standard Control / In-Office Monitoring)

Dear Ms. [last name],

Thank you for being part of the Vanderbilt Fourth Trimester (V4) study. The V4 study will help us learn how to better care for women with high blood pressure in pregnancy.

You have been assigned to the following interventions:

1. Blood pressure goal: <150/100

From discharge through 6 weeks postpartum, we recommend that your blood pressure be less than 150 mmHg systolic (top number) and less than 100 mmHg diastolic (bottom number). If either the top or the bottom blood pressure is higher than the target, your obstetric provider may consider starting or changing medications.

2. Blood pressure monitoring: Obstetric Provider

- You will be given an appointment to have your blood pressure checked in the office within 10 days of delivery. Usually you receive a MyHealth message about the appointment.
- For the first 2 weeks after delivery, you should check your blood pressure twice a day
- For weeks 3 to 6, you should check your blood pressure once a day
- If your blood pressures are over the goal above, contact your obstetric provider

3. Preeclampsia Danger Signs

Seek medical attention within an hour if you have any of the following:

- Blood pressure of 160 mmHg systolic (top number) or 110 mmHg diastolic (bottom number) after two blood pressure checks at least 15 minutes or more apart and within 4 hours
- A persistent headache that does not go away with rest, eating, or Tylenol
- Spots in your vision or difficulty seeing
- Difficulty breathing
- Persistent and worsening pain in your belly especially in the mid-upper or right-upper areas

4. Long-term Care

High blood pressure in pregnancy often goes away after delivery, but in some people it stays. Even if it goes away, having high blood pressure in pregnancy can make you higher risk for high blood pressure or heart disease later in life. You should see a primary care provider or cardiologist within 3 months after delivery to discuss ways to improve your heart health and to monitor your blood pressure. Be sure to tell your provider that you had high blood pressure in pregnancy.

Instructions for checking your blood pressure

1. Wait at least 30 minutes after smoking, eating, drinking caffeine (coffee, tea, soda), or exercising.
2. Sit comfortably at a table with both feet on the floor and your arm resting on the table, palm up.
3. Wrap the cuff around your arm, just above your elbow and not over clothing.
4. Push the button to inflate the cuff and record the blood pressure reading.
5. If the reading is above your goal blood pressure, wait 15 minutes and recheck it

If you have any questions or concerns about the study, please contact [name] at [contact]

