- **Enrollment:** After consenting to the study, participants will receive the initial survey via text web-link or email link. **Survey 1** asks questions about the participant's hypertension history, experience with prenatal care and care at delivery, and socio-demographic questions not reliably obtained from the electronic health record. We estimate that this survey will take 15 minutes to complete. Participants will receive a \$10 gift card for completion.
- **Randomization and Procedures before Hospital Discharge:** All participants will receive an Omron [validated blood pressure monitor](#) with appropriately sized cuff (Appendix A) following measurement of their arm circumference. Many of our patients do not obtain blood pressure cuffs postpartum, and they infrequently are covered by insurance providers. Instructions for blood pressure measurements and discharge instructions will be discussed with the patient and sent via MyHealth messaging with the script described in Appendix B. Participants will be instructed to measure blood pressure after being seated for 10 minutes with legs uncrossed and back supported with their arm positioned at the level of their heart. They will be instructed to avoid caffeine and tobacco for 30 minutes prior to measuring blood pressure. If blood pressures reach a predefined target threshold (Interventions C and D), they should wait 15 minutes and repeat the blood pressure measurement. Participants will be instructed to bring their blood pressure cuff to their first follow up appointment for calibration and clinical correlation. At hospital discharge, participants will receive information regarding follow up after HDP: a) seeking care for sustained severe blood pressures ($\geq 160/110$ mmHg at least 15 minutes apart), b) preeclampsia alert symptoms (headache, confusion, or visual changes), and c) scheduling an appointment with a primary care clinician at 3 months postpartum. All patients will receive a written letter explaining the study (Appendix C) that they can take to clinician visits outside the VUMC system. At discharge, a follow up in-person visit for a blood pressure check within 7-10 days postpartum will be requested by the inpatient team, which is our routine practice. Our specific research interventions are:

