APPENDIX J

STANDARD blood pressure control treatment algorithm:

[figure not shown]
V4 Postpartum Hypertension Management Guidelines **STANDARD CONTROL**

Monitoring Frequency

- Weeks 1-2: daily
- Weeks 3+: weekly

How: Seated for 10 minutes, arm at heart level

- If $>150/100$, wait 15 minutes and recheck
- Record second blood pressure

Antihypertensive Medication Escalation Plan:

Nifedipine XL: 30mg daily, 60mg daily, 90mg daily, 120mg daily
Labetalol: 200mg BID, 400mg BID, 600mg TID, 800mg TID
SBP = Systolic Blood Pressure | DBP = Diastolic Blood Pressure

Alert Symptoms:

Headache, visual changes, difficulty breathing, abdominal pain, sudden weight gain

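### The participant scripts (Appendices B–E) do not match the protocol body on rest, back support and confusion, and leave the handling of repeat readings open

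*Combined protocol and SAP*

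**What the plan says.** **Protocol body.** Study Procedures (Randomization and Procedures before Hospital Discharge) requires measurement while "seated for 10 minutes with legs uncrossed and back supported with their arm positioned at the level of their heart". The measurement and discharge instructions "will be discussed with the patient and sent via MyHealth messaging with the script described in Appendix B". On repeats it says: "If blood pressures reach a predefined target threshold (Interventions C and D), they should wait 15 minutes and repeat the blood pressure measurement". The same section lists three alert symptoms for the discharge information: headache, confusion and visual changes.

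**Participant scripts.** Appendices B, C, D and E carry the same five measurement steps. Step 2 reads: "Sit comfortably at a table with both feet on the floor and your arm resting on the table, palm up". Step 4 reads: "Push the button to inflate the cuff and record the blood pressure reading". Step 5 reads: "If the reading is above your goal blood pressure, wait 15 minutes and recheck it". The danger signs calling for care within an hour are severe blood pressure on two checks, headache, visual problems, difficulty breathing and abdominal pain.

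**Treatment algorithms.** Appendix J (standard control) has "If $>150/100$, wait 15 minutes and recheck", followed by "Record second blood pressure". Appendix K (tight control) is the same with a trigger of 140/90. Both keep the ten-minute seated rest and the arm at heart level.

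**Outcome derivation.** In the variable table under Outcomes, SBP710 and DBP710 take the in-person value if there is one and otherwise the remote value. If several remote values were submitted, the day-8 values are averaged. Nothing says which member of a first-and-repeat pair enters that average.

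**The concern.** The script is the written reference a participant keeps for six weeks of home measurement, and it is less complete than the protocol that describes it. Three things follow.

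- Home readings in the remote groups drive drug titration, and they stand in for the 7–10 day value when no office reading exists. They may be taken without the rest and back support that the protocol intends.
- The script tells the participant to record the first reading and then merely to recheck, while the algorithm pages ask for the second. The recheck trigger is the assigned goal, so a first systolic reading between 140 and 150 is repeated under tight control only. Depending on which reading is kept, home-sourced values in groups #3 and #4 could be formed by different rules.
- A neurological alert symptom that the protocol undertakes to communicate is absent from the message.

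**Working it through.** **Text comparison.** The plan gives no figure to reproduce here. Its six measurement elements compare with the scripts as follows; the result is the same in 4 of 4 scripts.

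| Element in Study Procedures | Appendices B–E |
|---|---|
| Ten-minute seated rest | absent |
| Back supported | absent |
| Legs uncrossed | approximated (feet on floor) |
| Arm at heart level | approximated (arm on table) |
| 30-minute wait after caffeine or tobacco | stated |
| 15-minute wait, then repeat | stated |

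That is 2 stated, 2 approximated and 2 omitted. The 30-minute wait in step 1 follows smoking, eating, caffeine or exercise and is not a seated rest.

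All three symptom lists differ. The protocol body has confusion. The scripts lack it but add breathing difficulty and abdominal pain. Appendices J and K also lack it and add sudden weight gain.

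**How many first readings fall between the two triggers.** Inputs from Power and Sample Size Considerations: SBP mean 138, SD 17.2; DBP mean 83, SD 11.9. Assumed: normal distributions, and that these values apply to home readings.

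- P(140 < SBP ≤ 150) = Φ(12/17.2) − Φ(2/17.2) = 0.757 − 0.546 = 0.211.
- P(90 < DBP ≤ 100) = Φ(17/11.9) − Φ(7/11.9) = 0.923 − 0.722 = 0.202 (from unrounded values).

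About one first reading in five on each component falls where its own value prompts a repeat in the tight group only.

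**Effect on SBP with no true difference between goals.** Let s be the SD of a single reading around the person's own level, assumed to be 4, 6 or 8 mmHg (not in the documents), with total SD fixed at 17.2. If the repeat replaces the first, regression to the mean gives

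tight minus standard mean = −(s²/17.2) × [φ(2/17.2) − φ(12/17.2)] = −(s²/17.2) × (0.3963 − 0.3128).

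This is −0.08, −0.17 and −0.31 mmHg for s = 4, 6 and 8. The share at or above 140 was simulated with 2 million persons, two day-8 sessions and a systolic trigger only:

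| Rule for the pair | Mean difference (mmHg), s = 4 / 6 / 8 | Share ≥140, tight minus standard (points) |
|---|---|---|
| Repeat replaces first | −0.08 / −0.18 / −0.31 | −3.7 / −4.5 / −4.5 |
| All day-8 readings pooled and averaged | −0.02 / −0.04 / −0.06 | about −0.6 to −0.9 |
| Averaged within session, then across sessions | −0.04 / −0.09 / −0.16 | about −1.8 to −2.8 |
| First reading only | 0 | 0 |

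**Dilution.** These figures apply only to home-sourced values, whose number is not given. If 20–40% of remote-group values are home-sourced (assumed), the worst case becomes 0.20 × 4.5 = 0.9 to 0.40 × 4.5 = 1.8 points between groups #3 and #4. Over the whole goal comparison, where only half the participants are in remote groups, it is about half that: 0.5 to 0.9 points.

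**The case against.** The strongest reply is that no measurement standard is missing. The protocol states it in full, says the instructions are discussed as well as sent, and promises discharge information that includes confusion; the scripts are shorter reminders. This stands in part. Oral teaching may cover the gap, but the written text is what participants consult later.

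On recording, step 5 can be read as repeating step 4. Appendices D and E tell participants to log their pressures daily, and the wording in J and K can mean that the second reading is recorded as well as the first. All this is plausible, and the algorithm figures are not available to settle it. But no text says which reading counts. Even averaging has two readings, which give different results in the table above.

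A reader might infer that the goal-specific trigger biases the trial in favour of tight control. The documents do not support that. The co-primary SBP and DBP are in-office. The replacement rule is one possible reading, not a stated one. The variable affected, SBP710 at or above 140, is derived under Outcomes but is not a Table 3 outcome. A goal-based recheck is also deliberate. Nor can one infer that the missing rest or back support biases the comparison in a known direction: the wording is identical in all four scripts, and the documents allow no size or sign to be given.

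**Conclusion.** The point holds as a minor inconsistency between documents. In all four scripts the seated rest, the back support and confusion are missing, and the handling of the repeat reading is left open; this rests on text comparison alone and is firm. The consequence is limited to home readings: titration in the remote groups, and SBP710/DBP710 (with the analysis that adds remote values) when there is no office value.

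The numerical consequence is conditional. It needs the repeat to replace the first, normality, planning values that carry over to home readings, an assumed repeat-reading SD of 4–8 mmHg and a systolic-only trigger. On those terms the share at or above 140 is at most about 4.5 points lower among home-sourced values, or roughly 1–2 points between groups #3 and #4 at the assumed 20–40%. The mean shift of 0.1 to 0.3 mmHg is negligible against the 4 mmHg that the plan is powered to detect.

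**What to change.** - Appendices B–E, step 2: add the ten-minute seated rest, the supported back and the arm at heart level.
- Appendices B–E, step 5: tell participants to record both the first and the repeat reading. Table 3 defines severe hypertension on two readings, so keeping only one of a pair would discard relevant information. The plan does not say how home readings feed that outcome.
- Appendices J and K: change the instruction so that both readings are recorded.
- SBP710/DBP710 derivation: state one rule, the same for every goal group, for which reading enters the day-8 average. Taking the first reading of each session is one option and removes the dependence on the goal-specific trigger.
- Danger-sign lists in B–E and alert symptoms in J and K: add confusion.

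The cost is edits to four message templates and two algorithm pages, one sentence in the derivation, and notification of the IRB. Sample size, visits and analysis model do not change.
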